## PROTOCOL SYNOPSIS

Protocol Title:	A Dose Escalation Study to Evaluate the Effect of Inhaled Nitrite on Cardiopulmonary Hemodynamics in Subjects with Pulmonary Hypertension	
Protocol Number:	PRO 11080686	
NCT Number:	NCT01431313	
Version # and Date:	Version 3.0/October 12, 2017	
Clinical Phase:	Phase II clinical investigation	
Investigational Drug:	Sodium Nitrite Inhalation Solution (AIR001 Inhalation Solution)	
Trial Site:	Single-Center Trial	
Sponsor:	[name] Associate Professor of Medicine University of Pittsburgh Heart and Vascular Institute	
Investigator:	[name], MS, FACC Associate Professor of Medicine University of Pittsburgh UPMC Heart and Vascular Institute	
Sub-Investigators:	[name] [name]	[name] [name] [name]
Study Monitor:	[name] Associate Professor of Medicine University of Pittsburgh Heart and Vascular Institute	
Research Facilities:	University of Pittsburgh Medical Center [name]	

Clinical Laboratories:	University of Pittsburgh Medical Center [name]
Manufacturer:	Aires Pharmaceuticals, Inc.
Study Rationale:	
Inhaled nitric oxide has been demonstrated to improve pulmonary hemodynamics in subjects with pulmonary arterial hypertension (PAH).
 
We hypothesize that inhaled nitrite provides a therapeutic approach for patients with PAH for the following reasons:
 

1. Inhaled nitrite therapy provides a potent, effective treatment that will vasodilate the pulmonary circulation (reduce pulmonary vascular resistance), reduce mean pulmonary artery pressure, and increase cardiac output.

2. This study will provide valuable efficacy and safety insights into the interactions between NO and nitrite, both direct NO generators, with or without background PH therapy, particularly phosphodiesterase type-5 inhibitors (PDE-5I), on pulmonary hemodynamics and right heart function.

3. This study will also provide novel assessments of right ventricular global myocardial function.

4. The results obtained from this study will also lay the groundwork for future large-scale clinical trials that are needed to investigate the efficacy of inhaled nitrite and/or its long-term effects on pulmonary hemodynamics in patients with pulmonary hypertension.

Study Objectives:	The main objective of this study is to investigate the effect of inhaled nitrite delivered in a dose escalation manner in patients that may be on background pulmonary hypertension therapy; endothelin receptor antagonist (ETRA), PDE-5I, or prostacyclin analog on cardiopulmonary hemodynamics in subjects with pulmonary hypertension.
Study Hypothesis:	

• We hypothesize that inhaled nitrite treatment will improve clinical parameters of pulmonary vascular and right heart function. Our primary endpoint will be the change in pulmonary vascular resistance (PVR) measured by right heart catheterization.

• We hypothesize that inhaled nitrite treatment will improve global right ventricular function.

	
 
• We hypothesize that inhaled nitrite may be delivered safely, based on stable mean arterial blood pressure with minimal dose limiting symptoms, in patients on background PAH therapy, particularly PDE-5I (sildenafil, tadalafil).
 

Study Aims:
	
Specific Aims:
 
 
1. To determine the efficacy of inhaled nitrite, on the change in pulmonary vascular resistance measured by right heart catheterization.
 
2. To explore the effect of inhaled nitrite on echocardiographic and hemodynamic parameters measured: SVR, RV systolic (dP/dtmax/IP, PWRmax/EDV, RV EF, TAPSE), RV diastolic function (dP/dtmin, Tau), Pulmonary vascular impedance / Wave Intensity.
 
3. To evaluate the safety of inhaled nitrite on systemic blood pressure in patients on background therapy for PAH.
 
4. To identify the pharmacokinetic relationships of nitrite measures of drug exposure and plasma cGMP, using blood sampling.
 
5. To identify the changes in mitochondrial oxygen consumption, using analysis of platelets.
 
6. To compare effects of inhaled nitrite on pulmonary vascular resistance with inhaled NO gas at 40 ppm.
 

	
This is a single-center, open label phase II study to evaluate the effect of inhaled nitrite delivered in a dose escalation manner on the change in pulmonary vascular resistance (PVR) in subjects with pulmonary arterial hypertension undergoing right heart catheterization.
 
A total of 50 subjects with a confirmed diagnosis of pulmonary hypertension and meeting all inclusion/exclusion criteria will be enrolled in the study which will entail a single right heart catheterization. The study population consisted of subjects with WHO group I PAH (n=20), WHO group II PH (n=20) and subjects with WHO group III PH (n=10) will receive the dose escalation paradigm:
 
 
• Each subject will receive a starting dose of 45 mg inhaled nitrite (AIR001 Inhalation Solution), followed by a second dose of 90 mg inhaled nitrite, based on safety and tolerability.
 

The study visit will occur on the same day subjects are scheduled for their clinically indicated right heart catheterization or who volunteer for a research right heart catheterization for this specific study. Subjects on oral background PAH therapy (ETRA or PDE-5I) will be instructed to hold their regular PAH regimen on the day of the study visit.

Baseline pulmonary artery hemodynamic assessment, echocardiogram, micromanometry measured simultaneous pressure and flow velocity signals will be performed prior to inhaled nitrite treatment. Responses to 40 ppm inhaled NO will be measured before nitrite nebulization via a non-rebreather face mask to assess baseline, pre-AIR001 vasodilator responsiveness.

Subjects will receive a starting dose of 45 mg (placed in the nebulizer cup) of inhaled nitrite (AIR001), with one subsequent planned dose of 90 mg of inhaled nitrite, based on safety and tolerability, approximately 60 minutes after the first dose. During the study, right heart/pulmonary artery hemodynamics will be measured continuously, and cardiac output measured at 15 minute intervals, as well as noninvasive systemic blood pressure monitoring. Subjects will be tested for the changes in hemodynamics and calculated pulmonary vascular resistance (PVR) with inhaled nitrite.

Subjects will be monitored closely for changes in blood pressure during the study. The presence of severe systemic hypotension defined as systolic blood pressure >30 mm Hg drop from pre-dose baseline AND symptomatic or requiring fluid replacement or other therapy will lead to a discontinuation of the study treatment, and the next higher dose of inhaled nitrite will not be administered. Subjects will continue to be monitored closely.

Oxygen saturation measured by pulse oximeter and methemoglobin levels monitored by co-oximetry prior to dose administration and through 2 hours post-dose will be monitored closely.

Blood samples may be collected for Cyclic Guanosine Monophosphate (cGMP) concentration determination, pharmacokinetics (PK) and platelet mitochondrial analysis at pre dose and the end of the each peak dose of nitrite (approx. 15 minutes post inhaled dose). PK and cGMP measurements will be made on mixed venous blood using PCW pullback samples and venous blood will be collected for platelet mitochondrial analysis.

Subjects will be monitored carefully for occurrences of adverse events, laboratory test abnormalities, and changes in vital signs.

	
Following the study treatment, patients will be followed as an outpatient on Day 30 (+/- 5 day window). An additional follow-up assessment by telephone will occur on Day 3.

Planned Sample Size:	50 subjects
Duration of Treatment:	One day
Inclusion Criteria:	
WHO Group I PAH (n = 20)          Diagnosis of RHC confirmed WHO Group I PAH in any of the following 3 categories:
 
 
• Idiopathic, primary or familial pulmonary arterial hypertension (IPAH, PPH, or FPAH)
 
 
OR
 
 
• PAH associated with one of the following connective tissue diseases (CTD):             
 
i. Systemic sclerosis (scleroderma)
 
ii. Limited scleroderma
 
iii. Mixed connective tissue disease
 
iv. Systemic lupus erythematosus
 
v. Overlap syndrome;
 
 
 
 
OR
 
 
• PAH associated with:             
 
i. Human immunodeficiency virus (HIV) infection;
 
ii. Simple, congenital systemic-to-pulmonary shunts at least one year post-surgical repair.
 
iii. Exposure to legal drugs, chemicals and toxins, such as fenfluramine, derivatives, other anorexigens, toxic rapeseed oil or L-tryptophan. Subjects with PAH associated with illegal drug use, such as methamphetamine, are excluded.
 
 
 
 
Stable PH for at least 3 months if on disease specific therapy.
 
WHO Group II PH (=20)  Diagnosis of RHC confirmed WHO Group II PH by:
 
 
• Pulmonary capillary wedge pressure (PWCP) > 15
 
 
AND
 
 
• Transpulmonary Gradient (TPG) > 12
 
 
WHO Group III PH (n = 10)          Has WHO functional class II-IV symptoms          Had the diagnosis of PH confirmed by a cardiac catheterization with the following values:
 
 
○ Mean pulmonary artery pressure (mPAP) ≥ 25 mm Hg (at rest)
 
○ PCWP or left ventricular-end diastolic pressure ≤15 mm Hg (if diagnosed with PAH)
 

	
 
○ Pulmonary Vascular Resistance (PVR) <math>\geq</math> 3 mm Hg/L/min or <math>\geq</math> 240 dynes*sec/cm^5
 
 
Both WHO Group I PAH, WHO Group II and III PH
 
 
1) Age 18 and older;
 
2) Able to participate in right heart catheterization
 
3) Evidence of a personally signed and dated informed consent document indicating that the subject has been informed of all pertinent aspects of the study
 
4) Subjects who are willing and able to comply with scheduled visits, treatment plan, laboratory tests, and other study procedures
 


Exclusion Criteria:
	
 
• Age less than 18 years;
 
• Baseline systemic hypotension, defined as MAP less than 50 mmHg;
 
• Required intravenous inotropes within 30 days prior to study participation;
 
• Has uncontrolled systemic hypertension as evidenced by sitting systolic blood pressure >160 mm Hg or sitting diastolic blood pressure >100 mm Hg at screening;
 
• Has a history of portal hypertension or chronic liver disease, including hepatitis B and/or hepatitis C (with evidence of recent infection and/or active virus replication) defined as moderate to severe hepatic impairment (Child-Pugh Class B-C);
 
• Has chronic renal insufficiency as defined by serum creatinine >2.5 mg/dL at screening or requires dialysis support;
 
• Has a hemoglobin concentration <9 g/dL at Screening;
 
• History of atrial septostomy within 6 months prior to Day 1 visit
 
• Repaired or unrepaired congenital heart disease (CHD);
 
• Pericardial constriction;
 
• Confirmed diagnosis of restrictive or constrictive cardiomyopathy;
 
• Left ventricular ejection fraction (EF) <40% by multiple gated acquisition scan (MUGA), angiography or echocardiography;
 
• Symptomatic coronary disease with demonstrable ischemia;
 
• Other severe acute or chronic medical or laboratory abnormality that may increase the risk associated with study participation or investigational product administration or may interfere with the interpretation of study results and, in the judgment of the investigator, would make the subject inappropriate for entry into this study;
 
• Has a psychiatric, addictive or other disorder that compromises the ability to give informed consent for participating in this study. This includes subjects with a
 

	
recent history of abusing alcohol or illicit drugs 30 days prior to study screening Day 0 and for the duration of the study;
 

• Poorly controlled asthma defined by active wheezing and/or cough with FEV1 < 70% predicted, responsive to inhaled BD (>15% increase in FEV1 with BD);

• Investigators, study staff or their immediate families;

• Clinically significant intercurrent illness (including lower respiratory tract infection) or clinically significant surgery within 4 weeks before the administration of study drug;

• Personal or family history of congenital or acquired methemoglobinemia;

• Personal history of RBC CYP B5 reductase deficiency;

• Known or suspected hypersensitivity or allergic reaction to sodium nitrite;

• Personal history of glucose-6-phosphate dehydrogenase (G6PD) deficiency or any contraindication to receiving methylene blue;

• If female, is pregnant or breast feeding, or has a positive urine or blood pregnancy test result predose;

• Receipt of an investigational product or device, or participation in a drug research study within a period of 15 days (or 5 half-lives of the drug, whichever is longer) before the first dose of study drug;

• Blood loss or blood donation >550 mL within 90 days or plasma donation >500 mL within 14 days before administration of study drug;

• RHC < 2 weeks from treatment visit unless clinically indicated

Study Endpoints:	
Primary endpoint: The primary outcome measures for this study is change in pulmonary vascular resistance measured by right heart catheterization from time zero compared with peak effect within 60 minutes post completion of nebulized dose of nitrite.
 
Secondary endpoints: The secondary endpoints measure:
 

• Time to maximum PVR decrease;

• Repeated measures ANOVA (RM-ANOVA) for change in PVR calculated from the start of inhalation and at times 15, 30, 45 and 60 minutes post end of nebulization.

• Change in mean pulmonary artery pressure, transpulmonary gradient and cardiac output (CO)/cardiac index (CI),

• Change in systemic blood pressure,

• Change in SVR, RV systolic (dP/dtmax/IP, PWRmax/EDV, RV EF, TAPSE), RV diastolic function (dP/dtmin, Tau),

- Change in pulmonary vascular impedance / Wave Intensity,
- Change in plasma nitrite concentrations in mixed venous blood at specified time points,
- Change in pulmonary artery occlusion (capillary) pullback nitrite and plasma cGMP at baseline compared with peak nitrite concentration.
- Change in mitochondrial oxygen consumption compared to baseline after each dose of nitrite.

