### 1.2 SPECIFIC AIMS

#### Hypothesis:

- We hypothesize that inhaled nitrite treatment will reduce pulmonary vascular resistance. Our primary endpoint will be the change in pulmonary vascular resistance (PVR) measured by right heart catheterization.
- We hypothesize that inhaled nitrite treatment will improve cellular and global right ventricular signaling and function.
- We hypothesize that nitrite will be safe and well-tolerated in patients on background PAH therapy (PDE-5I and ETRA)

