#### Specific Aims:

- 1) To determine the efficacy of inhaled nitrite, on the change in pulmonary vascular resistance measured by right heart catheterization.
- 2) To explore the effect of inhaled nitrite on echocardiographic and hemodynamic parameters measured: SVR, RV systolic (dP/dtmax/IP, PWRmax/EDV, RV EF, TAPSE), RV diastolic function (dP/dtmin, Tau), Pulmonary vascular impedance / Wave Intensity
- 3) To evaluate the safety of inhaled nitrite on systemic blood pressure in patients on background therapy for PAH.
- 4) To identify the pharmacokinetic relationships of nitrite measures of drug exposure and plasma cGMP, using blood sampling.
- 5) To identify the changes in mitochondrial oxygen consumption, using analysis of platelets

- 6) To compare effects of inhaled nitrite on pulmonary vascular resistance with inhaled NO gas at 40 ppm.

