### 1.3.5 Rationale for Dose of Nitrite

The low doses of nitrite used in these treatment regimens – less than 45 mg or 13% of the dose used in the emergency treatment of cyanide poisoning – do not produce methemoglobin levels greater than 3% and have not been associated with clinically significant hypotension. Aires Pharmaceuticals, who licensed intellectual property pertaining to inhaled nitrite from the NIH, has completed a Phase 1a single dose escalation study designed to define the maximum tolerated dose of inhaled sodium nitrite delivered to normal volunteers following electronic nebulization. These data, presented in abstract form at the 2009 ATS meetings, show that at the highest dose (176 mg) a significant decrease in systemic blood pressure and increase in heart rate was found. At the maximal tolerated dose (MTD);(125 mg) there was an increase in HR (+24 +/-5 bpm) without significant changes in systolic (-3 +/- 2 mmHg) or diastolic (-3 +/- 2 mmHg) blood pressure. Bioconversion of nitrite was demonstrated by an increase in exhaled NO. Methemoglobin levels increased at the highest doses administered, but remained less than 3.5% in all subjects. Pharmacokinetic modeling demonstrated dose-proportional increases in peak and AUC plasma nitrite.

Note that in 80 volunteers in phase I studies at the NIH methemoglobin levels never rose higher than 3%. If levels of methemoglobin rise above approximately 30% of total hemoglobin, a subject may appear cyanotic and experience dyspnea, due to the reduced oxygen carrying capacity of hemoglobin (methemoglobin cannot bind oxygen). Levels above 50% can cause seizures, hypotension, coma and death.

The effects of the interaction between FDA approved oral therapies for PAH (ETRA and PDE-5i) and inhaled nitrite are unknown. It is possible that the combination of the drugs

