could lower systemic blood pressure to potentially clinically significant levels. This is of particular concern for the PD5 inhibitors which will increase the levels of cGMP for any given dose of NO or nitrite. For this reason the doses have been reduced significantly below the MTD of 125 mg and a dose escalation plan will be followed with clear stopping rules. The patient will be carefully monitored with a pulmonary artery catheter during drug administration and intravenous fluids and vasopressors will be immediately available for the treatment of symptomatic hypotension. In addition we propose a dose escalation regimen to ensure careful drug dose titration.

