### **2.2 STUDY DESIGN AND METHODS**

#### **2.2.1. Study Design**

A total of 50 subjects with a confirmed diagnosis of pulmonary hypertension and meeting all inclusion/exclusion criteria will be enrolled in the study which will entail a single right heart catheterization. The study population consisted of subjects with WHO group I PAH (n=20), WHO group II (n=20) and subjects with WHO group III PH (n=10) will receive the following dose escalation paradigm: Each subject will receive a starting dose of 45 mg inhaled nitrite

(AIR001 Inhalation Solution), with one subsequent planned dose escalation of 90 mg inhaled nitrite, based on pulmonary vascular resistance response and safety and tolerability.

Screening (Day 0):

The potential study subjects are followed on a routine basis in the UPMC Heart and Vascular Institute (HVI), Comprehensive Lung Center (CLC) or an inpatient at UPMC Presbyterian, are well known or referred to the study investigator. Initial screening evaluations including physical examination, medical history, and clinical laboratory assessments will be conducted to determine study eligibilities during a routine clinic visit at the UPMC HVI, CLC or inpatient at UPMC Presbyterian. Subjects who meet the inclusion criteria and none of the exclusion criteria will be entered into the study.

Experimental Procedures (Day 1):

The study visit will occur on the same day subjects are scheduled for their clinically indicated right heart catheterization or who volunteer for a research right heart catheterization for this specific study. Subjects on oral background PAH therapy (ETRA or PDE5I) will be instructed to hold their regimen on the day of the study visit.

Subjects will be evaluated for additional medical history, physical examination, vital signs and pulse oximetry since screening. Laboratory testing will be repeated if baseline laboratory values are clinically significant and warrant repeat testing or inadvertently not collected at the screen visit. An echocardiogram with documentation of TRV for estimation of right ventricular systolic pressure and assessment of LV systolic and diastolic function will be performed pre and post nitrite inhalation.

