#### Risks of Sildenafil/Tadalafil (PDE-5 Inhibitor):

These medications are commonly used and FDA approved to treat Pulmonary Hypertension. These medications may lower blood pressure significantly if taken together with some other medications like nitroglycerin. AIR001 may cause similar effects in this study in combination with PDE-5I.

Subjects will be closely monitored throughout the entire procedure and should blood pressure drop significantly with the first inhaled dose of AIR001, study participant will not receive the next higher dose.

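### The safety hypotheses and Aim 3 concern patients on background PAH therapy, but oral ETRA and PDE-5I are held on the only dosing day; claim and exposure are not reconciled

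*Combined protocol and SAP*

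**What the plan says.** **The claim.** The Protocol Synopsis (Study Hypothesis) expects safe delivery, judged by stable arterial pressure and few dose-limiting symptoms, "in patients on background PAH therapy, particularly PDE-5I (sildenafil, tadalafil"). Section 1.2 restates this as "We hypothesize that nitrite will be safe and well-tolerated in patients on background PAH therapy (PDE-5I and ETRA"). Specific Aim 3, in the Synopsis and in Section 1.2, is "To evaluate the safety of inhaled nitrite on systemic blood pressure in patients on background therapy for PAH".

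**The reason for the claim.** Section 1.3.5: "The effects of the interaction between FDA approved oral therapies for PAH (ETRA and PDE-5i) and inhaled nitrite are unknown". On the possible fall in systemic pressure it adds: "This is of particular concern for the PD5 inhibitors which will increase the levels of cGMP", for any given dose of NO or nitrite. It gives this as the reason for doses below the maximum tolerated dose and for stepwise escalation. Section 5.1, on sildenafil and tadalafil, says: "AIR001 may cause similar effects in this study in combination with PDE-5I".

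**The conduct.** The Synopsis says subjects on oral ETRA or PDE-5I "will be instructed to hold their regular PAH regimen on the day of the study visit". Section 2.2.1 repeats that they "will be instructed to hold their regimen on the day of the study visit". The Synopsis gives the duration of treatment as one day.

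**The analysis.** Section 2.15.2 plans a t-test of baseline against the highest tolerated dose, repeated-measures ANOVA for secondary endpoints, and adverse-event tables by body system, severity and relatedness. None is split by background therapy.

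**The concern.** The two oral classes named in the Section 1.2 safety hypothesis are exactly the two that are held. The mechanism in Section 1.3.5 needs the PDE-5 inhibitor to be present when nitrite arrives. If that day's dose is withheld, the trial observes chronically treated patients at some lower, unrecorded level of the drug. That differs from nitrite given on top of a current dose.

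The stake is interpretation. Few hypotensive events could be taken as support for safety with PDE-5I in general. The error would run in the reassuring direction, and Section 1.4 says the results will prepare the ground for large later trials.

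**Working it through.** This is mainly a check of consistency, and no stated figure in the plan needs reproducing.

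**Step 1: what is claimed against what is given.**

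| Statement | Therapy named | Held on the dosing day? |
|---|---|---|
| Synopsis safety hypothesis | Background PAH therapy, PDE-5I singled out | Oral PDE-5I: yes |
| Section 1.2 safety hypothesis | PDE-5I and ETRA | Oral forms: yes, both classes |
| Aim 3 | Background therapy for PAH, no class named | Oral ETRA and PDE-5I: yes; other classes not stated |
| Section 1.1 objective | ETRA, PDE-5I or prostacyclin analog | Prostacyclin analog not named in the hold |
| Sections 1.3.5 and 5.1 | Oral ETRA/PDE-5I interaction; combination with PDE-5I | Yes |

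The mismatch is complete for oral ETRA and PDE-5I. It is not shown for prostacyclin analogs.

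**Step 2: can the data repair it afterwards?** Sections 2.12.5 and 2.12.8 collect concomitant medications as covariate information, so the background drug should be known. No section asks for the time of the last dose, sets a washout length or measures a background-drug level. Section 2.10.3 reviews medication changes, but by telephone on Day 3. The Group I criteria make therapy conditional (stable for three months *if* on it), and no minimum number of PDE-5I users is set. Section 2.15.2 never separates users from non-users.

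**Step 3: how undefined is the exposure?** The documents give no half-life or dose timing, so both are assumed here.

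Residual fraction = 0.5^(hours since last dose ÷ half-life)

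- 4 h half-life, 36 h gap: 0.5^9 = 0.2%
- 4 h half-life, 24 h gap: 0.5^6 = 1.6%
- 18 h half-life, 24 h gap: 0.5^1.33 = 39.7%
- 18 h half-life, 12 h gap: 0.5^0.67 = 63.0%

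The range, 0.2% to 63%, shows only that residual exposure could be nearly nothing or substantial, and that the plan would not know which.

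**Step 4: a separate limit from small numbers.** The number of PDE-5I users is not stated. With no events among n users, the one-sided 95% upper bound on the event rate is 1 − 0.05^(1/n): 31.2% for n = 8, 25.9% for n = 10 and 19.3% for n = 14. The values of n are assumptions. These bounds would be the same with or without the hold, so they illustrate small n and do not measure the mismatch.

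**The case against.** The strongest reply is that being on background therapy can mean chronic treatment and need not mean being dosed that morning. The hold sentence itself calls subjects on therapy while telling them to withhold it, and the eligibility criteria use the word in the same way. On that reading Aim 3 describes the patients actually studied. Section 1.3.5 justifies the dose and Section 5.1 discloses a risk; neither is a claim to be tested, and a precaution stays sound if some drug remains. This stands so far as Aim 3 goes: its wording is ambiguous rather than false. It does not explain how hypotheses naming the held classes, set beside a rationale about drugs acting together, are to be read once that day's dose is withheld.

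Some stronger inferences are tempting and are not supported:

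- *That there is no PDE-5I exposure.* A same-day hold is not a washout.
- *That Aim 3 singles out PDE-5I.* Only the Synopsis hypothesis does so.
- *That every background class is affected.* Prostacyclin analogs are not named in the hold.
- *That background drugs go unrecorded.* Concomitant medications are collected. The case report form is not among the documents, so it cannot be said to lack a last-dose field.
- *That the trial will declare the combination safe.* No such conclusion is written down.

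**Conclusion.** The point holds in limited form. The safety hypotheses and Aim 3, read with Sections 1.3.5 and 5.1, are not reconciled with the hold in the Synopsis and Section 2.2.1. At nitrite dosing, oral ETRA and PDE-5I exposure is reduced and undefined, and the analysis pools users with non-users. As planned, the trial can speak about chronically treated patients whose oral dose was held. It offers little on nitrite given with a current dose.

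No numerical size follows from the documents. The primary PVR comparison and the sample size do not depend on this point. The conclusion rests on the hold being followed as written and on no unseen document defining the time since the last dose or a split by background drug.

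**What to change.** 1. Reconcile the Synopsis hypothesis and aims and Sections 1.2, 1.3.5 and 5.1 with the hold in the Synopsis and Section 2.2.1. Whether therapy is held is for the sponsor and investigator; no view is taken here.
2. Word the safety claim to match actual exposure. If the hold stands, one form is: patients chronically treated with oral ETRA or PDE-5I whose dose was withheld on the study day. State separately what applies to prostacyclin analogs.
3. Record the drug, dose and clock time of the last dose before nitrite.
4. In Section 2.15.2, add a descriptive table of systolic pressure change and dose-limiting toxicities by background drug, allowing for combinations and for no therapy. List time since last dose by subject. Do not model it, because the number of users may be small.
5. If zero-event bounds are reported, give the number of users and present them as a limit of small n.

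The cost is revised wording, a last-dose entry in the data collection if it is not already there, and one table. The downside is a narrower safety conclusion.
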